**Full assessment of joints**

The course of psoriatic arthritis should be assessed with tender/swollen joint counts (68/66).

Physician's and patient's assessment of the disease activity and patient's assessment of pain are performed using the visual analog scales (VAS). The scales developed for this study have no gradings. The patient/physician should assess the item at his/her own discretion without using any measuring tools (ruler, etc.). It is prohibited to use the VAS for pain/disease activity that was already used at the prior visit (either for patients or for physicians). The VAS must not be given to patients for completing at home. They must be filled at the study site on the visit day. Completed VAS must be stored in the Investigator's File. The visual analogue scales are presented in Appendix 3.

[figure not shown]
Functional ability is assessed using HAQ-DI questionnaire filled in by the patient (Annex 4). The survey must be filled in only by the patient or his/her legal representative. The HAQ-DI

Translated from Russian to English, dated 26-Nov-2019  
questionnaires must not be given to patients for completing at home. They must be filled in at the study site on the visit day. Completed questionnaires should be stored in the Investigator's File.

[figure not shown]
The score is calculated in automatic mode when questionnaire data are recorded in the eCRF.

[figure not shown]
[figure not shown]
#### **4.7.14. Diagnostics of depression**

[figure not shown]
This study uses Beck's Depression Inventory to evaluate depression. Beck's Depression Inventory consists of 21 groups of statements of the most common symptoms and complaints. Each group contains 4 to 5 statements referring to specific signs/symptoms of depression. Statements within one group are ranged from having the lower to the higher impact of the symptom to the overall depression severity.

Clinical Study Report  
Protocol ID: BCD-085-7  
Appendix 1.  
Translated from Russian to English, dated 26-Nov-2019

Results processing:

The value of each category is calculated the following way: each item is scored from 0 to 3 depending on the increase or decrease of the symptom severity. The total Beck Inventory score is from 0 to 62 (the lower the score the better the health state).

Interpreting the Beck's Depression Inventory

Translated from Russian to English, dated 26-Nov-2019

[figure not shown]
Test results are interpreted as follows: 0-9 - no signs of depression; 10-15 - minimal depression (sub-depression); 16-19 - mild depression; 20-29 - moderate depression; 30-63 - severe depression.

The test is performed by the patient at screening and Visit 22 (Week 54).

Patients who scored 16 and more in the Beck's Depression Inventory are not included in the study.

#### **4.7.15. Blood drawing for immunogenicity testing**

Immunogenicity will be assessed by detecting binding and neutralizing antibodies in patients' serum. The test for binding antibodies to BCD-085 will be conducted at the Central Laboratory (JSC BIOCADC's Separate Subdivision) with validated ELISA procedures. The assay for neutralizing antibodies to BCD-085 will be performed only if the test for binding antibodies shows positive results. The neutralizing Abs assay will be done at the Central Laboratory (JSC BIOCADC's Separate Subdivision) with a validated ELISA protocol.

Translated from Russian to English, dated 26-Nov-2019

Do not use hemolyzed (bright red) or lipemic (milk-white) serum specimens, or serum specimens with a sediment after spinning.

A courier service authorized by JSC BIOCAD will deliver samples to the central lab, maintaining the temperature regimen (on dry ice).

After the study closeout, the retained samples may be destroyed according to the study site's SOPs.

The first blood sample will be taken on Visit 1 before the injection of the investigational product. Starting from Week 64, time points for blood drawing for immunogenicity testing will differ between patients from Arms 1/2 and 3. Therefore, during the extension study period, the label will also contain study week number (for example, IG4-1A64).

#### **4.7.16. Storage and shipping of biospecimens**

Serum specimens should be stored at the study site until they are shipped to the central laboratory. Specimens will be shipped to the central lab by batches after patients assigned to this

Translated from Russian to English, dated 26-Nov-2019

study site provide all blood samples specified by the Protocol and the CRA checks the availability of all required samples during the routine monitoring visit. [REDACTED]

[figure not shown]
[REDACTED] All shipments to the central laboratory will be made via a delivery service. Contact information of the courier company and central laboratory will be provided by the study CRA.

Before shipping the specimens, the member of the study team should notify the analytical laboratory staff and agree upon the shipping date by phone.

#### 4.7.17. Total blood volume taken during the study

Table 39 gives the estimated volume of blood to be taken at each visit and during the entire study.

**Table 39.** Volume of blood to be taken from each subject in the study.

Visit	Laboratory tests (frequency / blood taken per 1 sample)	Total blood volume
Screening	
 
■
 
■
 
■
 
■
 
■
 
	

 TB diagnostics can be performed with the skin test (Diaskintest) or blood test (QuantiFERON/T-spot).

Visit	Laboratory tests (frequency / blood taken per 1 sample)	Total blood volume
Visit 1 (Day 1 of Week 0)		
Visit 6 (Day 1 of Week 8)		
Visit 8 (Day 1 of Week 12)		
Visit 13 (Day 1 of Week 24)		
Visit 14 (Day 1 of Week 26)		
Visit 16 (Day 1 of Week 34)		
Visit 18 (Day 1 of Week 42)		
Visit 21 (Day 1 of Week 52)		
Visit 22 (Day 1 of Week 54)		

Visit	Laboratory tests (frequency / blood taken per 1 sample)	Total blood volume
Visit 23 (Day 1 of Week 62)		
Visit 23-1  (Day 1 of Week 64)		
Visit 24 (Day 1 of Week 74)		
Visit 25 (Day 1 of Week 86)		
Visit 26 (Day 1 of Week 98)		
Visit 27 (Day 1 of Week 110)		
Visit 28 (Day 1 of Week 122)		

 Visits 23-1, 32-1, 32-2 are performed only in patients from Arm 3.

 Only for patients from Arms 1 and 2.

 Only for patients from Arms 1 and 2.

 Only for patients from Arm 3.

Visit	Laboratory tests (frequency / blood taken per 1 sample)	Total blood volume
Visit 29 (Day 1 of Week 134)		
Visit 30 (Day 1 of Week 146)		
Visit 31 (Day 1 of Week 154)		
Visit 32  (Day 1 of Week 158)		
Visit 32-1  (Day 1 of Week 166)		
Visit 32-2  (Day 1 of Week 170)		

 Only for patients from Arm 3.

 Only for patients from Arms 1 and 2.

[figure not shown]
 TB diagnostics can be performed with the skin test (Diaskintest) or blood test (QuantiFERON/T-spot).

 Visit 32 is performed only in patients from Arms 1 and 2.

 TB diagnostics can be performed with the skin test (Diaskintest) or blood test (QuantiFERON/T-spot).

 Visits 23-1, 32-1, 32-2 are performed only in patients from Arm 3.

Translated from Russian to English, dated 26-Nov-2019

Visit	Laboratory tests (frequency / blood taken per 1 sample)	Total blood volume
		
Total blood volume drawn from one subject over the entire study		For Arms 1 and 2: approximately 392 mL  For Arm 3: approximately 429 mL 

 If re-tests or additional tests are required, the total blood volume will not exceed 457 mL (for Arms 1 and 2) or 494 mL (for Arm 3).

#### **4.7.19. Assessment of the Patient's Diary**

The Patient's Diary is dispensed at Visit 22 (Day 1 of Week 54) and covers the whole extension study period.

The Investigator records in the Diary the contact details of the study site and the date of the next visit. The patient should be asked to document all injections in the Diary. If the patient has missed an injection, he/she should record this together with the reason. The patient should record all information about his/her health, including adverse events and their dynamics, and all medications he/she takes (study and concomitant therapies).

The Patient's Diary is checked and taken back at all scheduled visits. Pages withdrawn from the Patient's Diary should be kept as source documents.

#### **4.7.20. Data entering to eCRF**

The principal investigator and the study team members will be provided logins and passwords to enter the eCRF system.

The eCRF should be completed within 5 working days after the visit. All screening data should be entered at once after the screening.

In the eCRF system, patients are identified only with their unique Patient IDs. Screening ID can only be used until the patient is randomized in the study. After randomization, screening IDs must be changed to Patient IDs.

### **4.8. Stop rules and criteria for premature withdrawal for study subjects, study periods, and study as a whole**

#### **4.8.1. Stop rules for study as a whole**

The study may be stopped in the following situations:

1. JSC BIOCAD decides to stop the study due to safety reasons, ethical considerations,

2. Local ethics committees or regulatory authorities decide to stop the study.

#### **4.8.2. Criteria for premature withdrawal of study subjects**

The patient will be withdrawn from the study in the following circumstances:

1. Major violations of inclusion and/or exclusion criteria revealed after the enrollment (patients removed at the discretion of JSC BIOCAD).
2. The patient withdraws his/her consent to participate in the study.
3. The patient develops AEs or SAEs (including depressions), laboratory abnormalities or concomitant conditions that, in the investigator's opinion, make further participation in the study impossible, dangerous or non-beneficial regarding patient's well-being/safety.
4. During the main treatment period: The patient misses more than 2 injections (in this case, the patient's removal must be approved by JSC BIOCAD, refer to section 6.3.1. *Treatment compliance*) or misses 2 consecutive visits or 3 visits in total, or the patient regularly (7 times or more) violates the timing of the scheduled visits.
5. During the extension treatment period (Week 54 to Week 154 for patients from Arms 1 and 2, Week 54 to Week 166 for patients from Arm 3): if  $\geq 20\%$  injections are missed ( $\geq 5$  injections for patients initially randomized in Arms 1 or 2,  $\geq 6$  injections for patients initially randomized in Arm 3) or  $\geq 2$  consecutive visits/injections are missed;
6. The patient gets pregnant. If pregnancy is suspected, the urine test for HCG must be performed. If the test gives a positive result, the patient must be withdrawn from the study (follow-up procedures are described in section 5.4).
7. The patient is diagnosed with active tuberculosis during the treatment with the investigational product (the diagnosis should be confirmed by a documented impression from the TB Specialist);
8. The study is terminated by the decision of JSC BIOCAD, local ethics committees or regulatory authorities.
9. The patient uses medications prohibited by the Protocol.
10. The patient dies.

---

 Violation of eligibility criteria justified by the investigator and approved by the Sponsor is not a reason for removing the patient from the study.

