**ABBREVIATIONS**

AUC	Area under the concentration vs. time curve
AE	Adverse event
ALT	Alanine transaminase
AnSc	Anaphylaxis score
AP	Alkaline phosphatase
APTT	Activated partial thromboplastin time
AST	Aspartate transaminase
AUMC	Area under the first moment curve
BAbs	Binding antibodies
BCD-085	Monoclonal anti-IL17 antibody manufactured by JSC BIOCAD
BP	Blood pressure
BSA	Body surface area affected
CHF	Congestive heart failure
C 1	Total clearance
C max	Maximum drug concentration in the plasma
C min	Minimum concentration
CNS	Central nervous system
CRF	Case Report Form
CTCAE	Common Toxicity Criteria for Adverse Events
DLQI	Dermatology Quality of Life Index
DNA	Deoxyribonucleic acid
ESR	Erythrocyte sedimentation rate
GCP	Good Clinical Practice
GGT	Gamma-glutamyl transferase
GI	Gastrointestinal
GMP	Good Manufacturing Practice
HAQ-DI	Health Assessment Questionnaire Disability Index
HBcor	Hepatitis B core antigen
HBsAg	Hepatitis B surface antigen

HBV	Hepatitis B virus
HCG	Human chorionic gonadotropin
HCV	Hepatitis C virus
HDL	High-density lipoproteins
HIV	Human immunodeficiency virus
HR	Heart rate
ICH	International Conference on Harmonization
Ig	Immunoglobulin
IHC	Immunohistochemistry
IL	Interleukin
INN	International non-proprietary name
ITT	Intention-to-treat population (all patients who were randomized in the study, whether they completed the study per protocol or discontinued it due to any reason)
IU	International unit
JSC	Joint Stock Company
LDH	Lactate dehydrogenase
MAb	Monoclonal antibody
MRT	Mean residence time
NAb	Neutralizing antibodies
NAPSI	Nail Psoriasis Severity Index
NSAIDs	Non-steroidal anti-inflammatory drugs
NYHA	New York Heart Association
PASI	Psoriasis Area and Severity Index
PCR	Polymerase chain reaction
PD	Pharmacodynamics
PK	Pharmacokinetics
PP	Per-protocol population (all patients who completed the study per protocol)
Q2W	Once every 2 weeks
Q4W	Once every 4 weeks
RNA	Ribonucleic acid

SAE	Serious adverse event
SOP	Standard Operating Procedure
sPGA	Static Physician's Global Assessment
SS	Separate subdivision
t 1/2	Elimination half-life
TC	Total cholesterol
TNF- $\alpha$	Tumor necrosis factor alpha
TO	Thoracic organs
VAS	Visual analogue scale
Vd	Volume of distribution
WHO	World Healthcare Organization

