Any other therapy during the study	Any medications other than the investigational product that are used to perform the study procedures. This includes, for example, the drugs used as part of the combination therapy.
Patient's premature withdrawal (dropout)	The time point when the patient discontinues the study before the planned completion of the study therapy and/or assessments. At this time point, the study therapy stops, and no further assessments are planned (follow-up for survival and/or disease progression may be an exception). If the patient discontinues the study due to an event planned by the Protocol (for example, a complete response), he/she is considered a dropout anyway.
Completion of the study	The time point corresponding to the final patient's visit.
Study therapy	Any medication or a combination of medications used in any arm as part of study procedures, including concomitant medications and introductory therapy before the active medication.
Concomitant therapy	Therapy with any drugs included in the study therapy, except for the test drug and reference drug. For example, drugs used for combination therapy, pre-medication etc.
Discontinuation of study therapy	Time point when the investigational therapy is terminated regardless of what caused the termination. It does not necessarily coincide with patient's withdrawal from the study.
Variable	An identifier used in data analysis; it is obtained directly or indirectly from data gained during the specified assessment within the specified time points.

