### **4.3. Measures to minimize/eliminate bias**

#### **4.3.1. Distribution of patients by study sites**

Patients' recruitment at the study sites will be performed on a competitive basis. Recruitment can be re-opened if the Sponsor's audit reveals patients who do not meet the eligibility criteria or patients with major Protocol violations (with no explanation timely provided to the Sponsor).

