**The investigator must inform JSC BIOCAD within 24 h about the patient's premature withdrawal and specify the reason.**

If the subject discontinues the study, an Early Withdrawal Form should be filled out in the CRF. The follow-up procedures for the discontinued subjects are described in section 5.4 *Procedures by Visits*.

Patients who discontinue the study will not be replaced.

For further details see Section 11.6. *Study termination*.

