**5.4.1. Follow-up of patients who received at least one dose of the investigational product**

The following should be done if the patient who received at least one dose of the investigational product discontinues the study early:

- On the day of withdrawal, the Early Withdrawal Visit should be conducted and the investigator should complete the Early Withdrawal Visit and the End of Study forms in the eCRF. The Protocol does not specify the amount of procedures to be performed during the Early Withdrawal Visit; this is to be determined on a case-by-case basis.

Said procedures are mandatory for all subjects who prematurely withdrew from the study, except for the subjects who are lost to follow-up or are physically unable to attend the visit. All records must be supported with appropriate source documents.

If the subject discontinues the study due to an AE/SAE, the investigator should conduct further treatment and follow-up after the Early Withdrawal Visit in accordance with the study site standards for the treatment of a certain AE/SAE. The patient is to be **followed up until the AE or SAE resolves completely**.

If a woman involved in the clinical study or a partner of a clinical study participant becomes pregnant, this does not need to be reported as an AE unless the baby has any congenital abnormality or birth defect (these should be recorded as SAEs). However, all pregnancies must be documented in a Pregnancy Report Form and reported to the Sponsor as soon as possible. Women who discontinued the study because of becoming pregnant during the study should be monitored throughout the entire pregnancy and 6 months after childbirth to evaluate the mother's and child's health. Such monitoring is performed when possible and requires patient's consent for the pregnancy follow-up. Information on pregnancy course and outcome should be recorded in the source documentation (with consent from the patient).

Information about the health of the patient prematurely withdrawn from the study must be recorded in the source documentation and eCRF.

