7. ANALYSIS POPULATIONS

Safety analysis

The safety analysis will include all patients randomized in the study (intent-to-treat (ITT) population).

Efficacy analysis

The efficacy will be assessed in the ITT (intent-to-treat) population, which includes all randomized patients. In addition, the efficacy can be evaluated in the PP (Per Protocol) population, which includes those patients who completed all visits without major protocol deviations.

Page 10 of 10

Immunogenicity analysis

The immunogenicity analysis will include all patients who have received at least one dose of BCD-085 and had an evaluable (not missing/lost/spoiled) serum sample taken before the first dose of BCD-085 and at least one evaluable (not missing/lost/spoiled) serum sample taken at subsequent visits.

Main demographics, baseline clinical and laboratory parameters obtained on the screening will be processed using descriptive statistics and will be analyzed in the efficacy and safety populations.

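### Withdrawing randomized patients for ineligibility at the sponsor's discretion, with no masking rule and no guaranteed Week 12 PASI, can create avoidable and possibly selective missing primary outcomes

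*Protocol*

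**What the plan says.** **Removal and retention.** Protocol 4.8.2 (repeated in 5.3) lists as the first withdrawal criterion "Major violations of inclusion and/or exclusion criteria revealed after the enrollment (patients removed at the discretion of JSC BIOCAD"). A footnote adds: "Violation of eligibility criteria justified by the investigator and approved by the Sponsor is not a reason for removing the patient from the study". No criterion or time limit separates the two outcomes. Section 11.3 also routes early-withdrawal decisions through the sponsor for approval.

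**Masking.** Section 4.3.5 blinds investigators and patients until Week 12. Under 4.3.4 the sponsor's Clinical Study Manager allocates the arm, unless the electronic system is used, and the sponsor keeps lists linking patients to arms. Under 4.10 it also stores one set of code envelopes.

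**Assessments after withdrawal.** The glossary entry on premature withdrawal says: "At this time point, the study therapy stops, and no further assessments are planned", with a possible exception for survival or progression follow-up. Section 5.4.1 nevertheless requires an Early Withdrawal Visit for dosed patients, unless they are lost or unable to attend. On its content: "The Protocol does not specify the amount of procedures to be performed during the Early Withdrawal Visit; this is to be determined on a case-by-case".

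**Analysis.** SAP section 7: "The efficacy will be assessed in the ITT (intent-to-treat) population, which includes all randomized patients". The Protocol's abbreviation list defines ITT as "all patients who were randomized in the study, whether they completed the study per protocol or discontinued it due to any reason". Protocol 9.6 and SAP 8.4 say missing data are not replaced.

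**Recruitment.** Section 4.3.1: "Recruitment can be re-opened if the Sponsor's audit reveals patients who do not meet the eligibility criteria or patients with major Protocol violations", followed by a parenthesis about the sponsor not having received a timely explanation. Sections 4.2 and 4.8.2: "Patients who discontinue the study will not be replaced".

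**The concern.** The primary endpoint is a single reading, PASI 75 at Week 12. A withdrawal that ends participation before that visit can remove the reading, and here the trigger is a decision taken after randomization. The eligibility facts themselves date from screening and are unrelated to the arm. The decision to act on them need not be, because it can be taken once treatment is under way by an organization that has access to the allocation and is under no stated duty to decide without it.

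Membership of the ITT set does not settle the matter. A patient can be in the set and still have no Week 12 PASI. With no substitution and no stated rule for such a patient, the primary proportion could be computed on those observed. Losing non-responders from the Q4W arm would then raise its rate and favour the non-inferiority claim, which is the main hypothesis.

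**Working it through.** **1. Planning figures.** Inputs from Protocol 9.3.1: Q2W rate 0.891, Q4W rate 0.826, margin 0.2038, alpha 0.05, power 80%.

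n per arm = (z₀.₉₅ + z₀.₈₀)² × [p₁(1−p₁) + p₂(1−p₂)] / (margin − difference)²
= (1.645 + 0.842)² × (0.0971 + 0.1437) / (0.2038 − 0.065)² = 77.3.

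The plan states 77, so its figure is reproduced with alpha one-sided. Then 77 × 1.1 = 84.7, giving 85 per active arm. At the planned rates, 85 patients yield 0.891 × 85 ≈ 76 responders on Q2W and 0.826 × 85 ≈ 70 on Q4W.

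**2. What a removal can do.** SAP 8.2 compares the lower 95% bound for Q4W minus Q2W with −20.38%. The documents do not name the interval method, so a Wald interval is assumed:

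lower = d − 1.96 × √[p₄(1−p₄)/n₄ + p₂(1−p₂)/n₂].

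Q2W is held at 76/85. Every removed patient is assumed to be a Q4W non-responder who drops out of the denominator.

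| Q4W counts | Removed | Difference | Lower bound | Against −20.38% |
|---|---|---|---|---|
| 70/85 (planned rate) | 0 | −7.1% | −17.5% | met |
| 70/80 | 5 | −1.9% | −11.7% | met |
| 66/85 | 0 | −11.8% | −22.8% | not met |
| 66/83 | 2 | −9.9% | −20.8% | not met |
| 66/82 | 3 | −8.9% | −19.7% | met |
| 66/81 | 4 | −7.9% | −18.6% | met |

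For the 66/82 row: √[0.8049 × 0.1951/82 + 0.8941 × 0.1059/85] = 0.0550, and −0.0892 − 1.96 × 0.0550 = −0.197.

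If the removed patients are instead counted as non-responders among all 85, the 66/85 bound stays at −22.8%.

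**3. How wide the sensitive zone is.** With up to four such removals, the conclusion changes only when Q4W has 65 to 67 responders out of 85:

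- 68/85 already meets the margin without removals (−20.1%).
- 67/85 moves from −21.5% to −19.4% with two removed.
- 65/85 moves from −24.1% to −20.0% with four removed.
- 64/85 still misses with four removed (−21.4%).

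**4. The passages side by side.** The glossary plans no assessments after withdrawal. Section 5.4.1 requires a visit but fixes none of its content. On either reading no PASI is secured, at withdrawal or at Week 12. For patients withdrawn before any dose, 5.4.2 asks only for a form unless there is an adverse event.

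**The case against.** The strongest reply is that the plan already protects the randomized comparison, and several parts of that reply stand.

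- A reader might infer that discretionary removal contradicts the all-randomized population. It does not: the ITT definition keeps patients who discontinue for any reason, and nothing takes a withdrawn patient out of the set.
- A reader might infer that removed patients are not assessed at all. For dosed patients 5.4.1 requires a visit and adverse-event follow-up. What is missing is a guaranteed PASI.
- A reader might take re-opened recruitment as replacement under another name. Section 4.3.1 does not say that added patients stand in for anyone, and its parenthesis on timely explanation narrows the trigger. Added patients would enter by the same stratified 2:2:1 block randomization, so unbalanced arms do not follow. The 213 in SAP section 5 is the planned number.
- A reader might infer that the person deciding knows the arm. That is not shown. Requests go to the Medical Advisory Division (11.3), while the Clinical Study Manager or the electronic system allocates. The retention footnote gives no timing, requires the investigator's justification, and may cover approvals given before randomization.
- Withdrawals are already documented: reason within 24 hours, a withdrawal form, and a sponsor decision within 48 hours.
- The illustration is one-sided by construction, and a rule counting missing outcomes as non-response would remove its effect on the bound.

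The last item does not dispose of the point. A non-responder rule fixes the denominator but does not recover the outcome, and a removed patient who would have responded is then counted as a failure. Separate units within the sponsor make arm-blind decisions feasible but do not require them.

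**Conclusion.** The point holds as a gap in safeguards. Following the plan as written, a sponsor decision with no masking requirement can end a randomized patient's participation before Week 12, with no primary outcome guaranteed and no rule for counting that patient. This can produce missing data that are avoidable and possibly related to arm and response. Nothing in the documents shows that the discretion would be misused.

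The numerical consequence is conditional. It needs removals concentrated among Q4W non-responders, exclusion of those patients from the denominator, and a Q4W result about five points below plan (66/85 = 77.6% against 82.6%). Three such removals then move the lower bound from −22.8% to −19.7%, across the margin. At the planned rates non-inferiority is met with or without removals. How often the discretion would be used cannot be known from the documents.

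The recruitment passages call for clarification: 4.3.1 and the no-replacement statements can both be true, but the plan does not say how.

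**What to change.** 1. In Protocol 4.8.2 and 5.3, state that, whatever is decided about treatment, a randomized patient later found ineligible is asked to attend Visit 8 for PASI and sPGA and is analysed in ITT. The violation is handled only in the PP set. The glossary already separates stopping study therapy from leaving the study, so no new concept is needed. Align the glossary entry on premature withdrawal with 5.4.1.
2. State that removal decisions before Week 12 are made by sponsor staff without access to the allocation, from screening data, and are logged with date and reason.
3. Reconcile 4.3.1 with 4.2 and 4.8.2 by saying that patients added after recruitment is re-opened replace no one and that all randomized patients are analysed.

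The cost is protocol wording and one already scheduled visit for a few patients. The downside is that a few ineligible patients contribute Week 12 data to ITT; the PP analysis shows their influence.
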